5.5 STRATEGIES FOR RECRUITMENT AND RETENTION

Framework: We will recruit individuals within participating practices and will randomize 360 participants into one of two arms within practices. We will have 2 study locations: the Chapel Hill catchment area and a catchment area in eastern North Carolina. Participants enrolled in the Chapel Hill catchment area (Waves 1 and 2, see below) will have their measurement visits conducted at Center for Health Promotion and Disease Prevention, located at [name]. Those randomized to the Med-South Weight Loss Program will have their face-to-face counseling visits at this office. The location for study visits for the eastern North Carolina catchment area is to be determined.

To insure PCPs will be familiar with the majority of patients identified as eligible using the EHR, only PCPs who have been at the practice for 10 or more months will be invited to participate. We will enroll participants in 3 sequential waves, with a sample goal of 120 participants for each wave, as outlined below:

- Wave 1: Enrollment to start late March or early April, 2020. Due to a hold on research activities related to the Covid-19 pandemic, the first participant was enrolled 6/12/2020.
 - Participating site is UNC Chapel Hill Internal Medicine Practice (academic practice).
 - All PCPs (attendings and residents) who have been at the practice for 10 or more months will be invited to review their panel listings of patients who qualify and make referrals to the study.
- Wave 2: Community practices in the Chapel Hill area defined as within 25 miles of our research office at [name]. Enrollment to no later than October, 2020. Originally our plan was to enroll 2 practices. However, after first contacts with practices, we have learned that at some only a sub-set of clinicians might participate. Realizing some will decline, there is no minimum number of participating clinicians required for the practice to participate. Depending on the number of PCPs who participate and their panel sizes, we may

need to recruit from more than 2 practices. Ultimately, we identified a 3rd practice for Wave 2 enrollment.

- Wave 3: Eastern North Carolina. Enrollment to start no later than April 2021. We anticipate working with 2 practices, but it may be more than 2.

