Questionnaires:						These data collected before the actual visit, on-line via REDCap or by phone. Window before baseline visit is 4 weeks. Window before follow-up and after follow-up visits is 2 weeks.
--Demographics and medical history (baseline only)	15	x				
--Diet assessment: diet quality, ¹⁴³ adapted PREDIMED checklist ^{19, 96}	10	x	x	x	x	
--Detailed assessment of diet quality: Willett Food Frequency Questionnaire ¹⁴⁴	20-30	x	x	x	x	
--Physical activity and sedentary behaviors: GPAQ for physical activity and sedentary behavior , ¹⁴⁵ participant report of monitored steps	5	x	x	x	x	
--Quality of life (EQ5D ¹⁴⁶)	5	x	x	x	x	
--Food insecurity ¹⁴⁷	2	x	x	x	x	
Diet Self-Efficacy Scale ¹⁴⁸	3	x	x	x	x	
Weight Loss Self-efficacy Short-Form (WEL-SF1) ^{149, 150}	3	x	x	x	x	
Early Self-Weighing Questionnaire ¹⁵¹	1	x	x	x	x	
Self-Regulation: Dietary Self-Regulation (TSRQ) ¹⁵²	3	x	x	x	x	
Three-Factor Eating Questionnaire ¹⁵³	3	x	x	x	x	
Mindful Eating Questionnaire ¹⁵⁴ **	5	x	x	x	x	

Perceived Stress Scale ¹⁵⁵	3	x	x	x	x	
PHQ-8 ¹⁵⁶	3	x	x	x	x	
--Medications for high BP, high blood lipids, diabetes, and weight loss (self-report with EHR review)	5	x	x	x	x	
--Adverse outcomes, CVD events, ER visits, and hospitalizations (follow-up only)	5		x	x	x	
--Acceptability (follow-up only)	5-10		x	x	x	
Diet and PA goals and success achieving goals (collected by web-based intervention platform and counselor)	NA					Collected after each counseling session in intervention group.
Exploratory Outcome						
Stool microbiome (participants may elect not to complete this measure)	NA	x	x	x	x	First sample will be collected in the 2 week period immediately after randomization. (These are the only baseline data collected after randomization.) The follow-up samples will be collected w/n a 2 week window of follow-up visit date.
Other						
--EHR to assess/confirm adverse health outcomes	NA		x	x	x	To confirm information collected by questionnaire at these visit time points

* <http://www.ncagr.gov/standard/Labs/>

**Added to baseline on 12/22/20. No follow-up data had been collected at this point in the study.

Note: table last updated 3/1/21

Additional Study measures—economic outcomes

The budgetary impact assessment and numerator for the cost effectiveness analysis will be based on Activity Based Costing Questionnaires previously developed and applied by [name] in similar studies^{99, 157} along with participants' health care claims data that will be used to compare resource

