9.4.2 ANALYSIS OF THE PRIMARY ENDPOINT(S)

The primary analysis will be conducted using the ITT Population and will be repeated secondarily using the Per Protocol Population.

Percent change in body weight = (Follow-up weight – baseline weight)/baseline weight x 100. We will compare the longitudinal mean % change in body weight between groups using analysis of covariance (ANCOVA), conducted using a linear mixed model. A mixed model will allow for the inclusion of all observed follow-up data for all participants. The model will include fixed effects for group, follow-up visit (4, 12, or 24 months), group-by-visit interactions, site, baseline weight, race/ethnicity, sex, and diabetes status. To account for within-participant correlation, the model will allow for correlated error terms using an unstructured covariance matrix. For the primary comparison, we will use an appropriately specified linear contrast of the model parameters to test for a treatment effect at 24-months at the 5% significance level. Secondarily, we will compare the groups at other time points and will estimate effect sizes along with 95% confidence intervals for each comparison. Secondarily, we will expand the model by including appropriate interaction terms, one at a time, to examine the potential heterogeneity of intervention effect in sub-groups, including diagnosis (diabetes vs. no diabetes), race/ethnicity, sex, and by degree of baseline obesity (BMI > 40 vs. less). Interaction terms will be tested at the 5% significance level.

We will use a longitudinal mixed effects logistic regression model to compare the groups for proportions losing > 5% body weight at each follow-up visit; estimates of odds ratios and 95% confidence intervals will be provided. This model will control for the same covariates specified for the primary model.

Missing Data

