9.4.3 ANALYSIS OF THE SECONDARY ENDPOINT(S)

Analysis of Secondary Objectives (1-2)

The ITT Population will be used in the primary analysis of all secondary outcomes. Similar ANCOVA methods to those described above will be used to compare groups on each of the secondary outcomes; for any outcome measured at baseline, the corresponding ANCOVA will control for baseline value in addition to the covariates noted above. Blood pressure will be averaged over three repeated measurements at each visit. Because they are of secondary interest, tests on secondary outcomes will each be conducted at the 5% significance level with no adjustments for multiple comparisons. All estimates of effect size will be accompanied by 95% confidence intervals. Data from all secondary outcomes will be presented regardless of extent of “significance”. Descriptive summaries of process data (attendance at intervention contacts, fidelity to intervention delivery, and acceptability of the Med-style dietary pattern) will be provided for participants randomized to Group 1 in the ITT Population. No inferential statistics (p-values or confidence intervals) will be presented.

Analysis of Secondary Objective 3 (Economic Analysis)

We plan to conduct both a budgetary impact assessment and a cost-effectiveness analysis. The budgetary impact assessment will quantify the total and per participant costs of intervention delivery from the health system perspective using an Activity Based Costing (ABC) approach and cost tracking forms that the health economist ([name])¹⁵⁸⁻¹⁶⁰ has developed and refined in past behavioral trials. Using this approach, all relevant labor, materials and supplies, contracted services, and other relevant costs required to deliver the interventions will be captured by key activities. This information will allow policy makers to identify the total and per capita fixed and variable costs of the intervention and to forecast required budgets, should the intervention expand beyond the trial phase. The non-sunk cost estimates will also feed into the cost-effectiveness analysis.

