### 9.4.4

### Secondary Analyses

The ITT Population will be used in the primary analyses of all secondary outcomes. Similar ANCOVA methods to those described in the primary outcome analyses will be used to compare groups on each of the secondary outcomes. For any outcome measured at baseline, the corresponding ANCOVA will control for baseline value in addition to the covariates noted above. Because they are of secondary interest, tests on secondary outcomes will each be conducted at the two-sided 5% significance level without adjustments for multiple comparisons. All estimates of effect size will be accompanied by 95% confidence intervals. Data from all secondary outcomes will be presented regardless of extent of "significance".

Descriptive summaries of process data (attendance at intervention contacts, fidelity to intervention delivery, and acceptability of the Med-South dietary pattern) will be provided for participants randomized to the Med-South dietary pattern intervention group in the ITT Population. No inferential statistics (p-values or confidence intervals) will be presented.

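### The Mindful Eating Questionnaire has no baseline score for early enrollees, and the baseline-adjusted ANCOVA gives no rule for keeping them in the analysis

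*Protocol*

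**What the plan says.** Protocol 8.1.2, Table 3, lists the "Mindful Eating Questionnaire" among the secondary-outcome questionnaires, with a mark at each of 0, 4, 12 and 24 months and no restriction to people who have a baseline score. The footnote to that row says "Added to baseline on 12/22/20. No follow-up data had been collected at this point in the study". Protocol 5.5 records that "the first participant was enrolled 6/12/2020".

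On analysis, Protocol 9.4.3 says "for any outcome measured at baseline, the corresponding ANCOVA will control for baseline value in addition to the covariates noted above", and SAP 9.4.4 repeats it: "For any outcome measured at baseline, the corresponding ANCOVA will control for baseline value in addition to the covariates noted above". Protocol 9.4.3 also says "The ITT Population will be used in the primary analysis of all secondary outcomes", and Protocol 9.3 and SAP 6.1 define that population as everyone randomized. The methods are to resemble those for weight, where Protocol 9.4.2 says "A mixed model will allow for the inclusion of all observed follow-up data for all participants". SAP 9.4.4 says the secondary tests will "each be conducted at the two-sided 5% significance level without adjustments for multiple comparisons".

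Neither document says what happens to a participant whose baseline value is missing. The missing-data text (Protocol 9.4.2, SAP 6.6) concerns dropout and missing follow-up weights. A missing-baseline rule exists only for blood work: Protocol 8.1.3.3a seeks no follow-up sample when there is no baseline sample.

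**The concern.** For this questionnaire the statements do not fit together. A regression that includes the baseline score as a covariate loses any participant who lacks that score, unless a rule says otherwise. The analysis would then cover later enrollees only, and the people lost would come from Wave 1, the academic practice. That is not an analysis of all randomized participants, and it sets aside follow-up scores that are valid for comparing the arms without a baseline.

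The stake is modest but real. Mindful eating is taught in the intervention (Protocol 6.1), and behavioral and psychosocial variables form Secondary Aim 2. The primary outcome and the key secondary outcomes in SAP 7.2 are not touched.

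**Working it through.** **Inputs.** Dates: Protocol 5.5 and the Table 3 footnote. Planned accrual of 20 per month and N = 360: Protocol 5.5. Detectable effect of 0.33 SD with 20% attrition, 80% power and alpha 0.05: Protocol 9.2 and SAP 9.6. Two assumptions are mine: the number *m* without a baseline score, and the baseline-to-follow-up correlation ρ = 0.5 to 0.7.

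**1. The gap.** 6/12/2020 to 12/22/2020 is 18 + 31 + 31 + 30 + 31 + 30 + 22 = 193 days, and 193/30.4 = 6.35 months.

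**2. How many.** At the planned pace, 20 × 6.35 = 127, and 127/360 = 35.3%. At half that pace it is about 63, and 63/360 = 17.5%. As a rough cross-check, Protocol 5.5 reports about 360 people invited by the end of Cycle 3 and expects about one quarter to join, which gives about 90. The end of Cycle 3 is not dated, so this is only indicative.

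**3. The plan's own figure.** n per arm = 360 × 0.8/2 = 144. Detectable difference = (1.96 + 0.842) × √(2/144) = 0.330 SD, which reproduces the stated 0.33.

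**4. The same formula without the early enrollees.**

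| m | n per arm | Detectable difference | Power for 0.33 SD |
|---|---|---|---|
| 0 | 144 | 0.33 SD | 80% |
| 63 | 297 × 0.8/2 = 118.8 | 0.36 SD | 72% |
| 127 | 233 × 0.8/2 = 93.2 | 0.41 SD | 61.5% |

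**5. What a better model recovers.** Let f = m/360 and consider one follow-up visit. Information on the arm effect, per unit of n, is:
- complete-case ANCOVA: (1 − f)/(1 − ρ²)
- a model that keeps everyone: (1 − f)/(1 − ρ²) + f

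The ratio of standard errors, complete-case to keep-everyone, is √[1 + f(1 − ρ²)/(1 − f)].

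- f = 0.353, ρ = 0.5: √(1 + 0.545 × 0.75) = 1.19
- f = 0.353, ρ = 0.7: √(1 + 0.545 × 0.51) = 1.13
- f = 0.175, ρ = 0.5: √(1 + 0.212 × 0.75) = 1.08
- f = 0.175, ρ = 0.7: √(1 + 0.212 × 0.51) = 1.05

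**6. Bias.** In a simulation of 3,000 trials (288 participants followed, one third without a baseline by order of enrolment, true effect zero), the mean complete-case estimate was 0.003 at both correlations, so there was no bias. At ρ = 0.5 its standard error was 0.1264, against 0.1025 with every baseline present (23% larger). A missing-indicator model, which keeps everyone, gave 0.108.

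**7. Which follow-up scores can exist.** The 12-month window opens at day 335 (SAP 5.4), which is 5/13/2021 for the first enrollee, so every 12- and 24-month visit falls after the questionnaire was added. The 4-month visit is less certain. SAP 5.4 gives a median of 154 days, which is 11/13/2020 for the first enrollee. If the footnote's statement about follow-up data refers to this questionnaire only, any 4-month visit held before 12/22/20 has no score. If it refers to the whole study, it fits poorly with that timing.

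**The case against.** The strongest reply is that the SAP may not analyse this questionnaire at all. SAP Table 1 and Appendix A do not name it. Their entry for eating behaviors cites the Three-Factor Eating Questionnaire, and the psychosocial objectives list other constructs. This stands as far as it goes: whether the measure is analysed is the first thing to settle. It does not remove the point, because Protocol Table 3 lists the measure as a secondary outcome and the objectives' list is introduced as non-exhaustive.

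Three stronger readings are tempting, and the documents do not support them.

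- **That the plan excludes everyone enrolled before 12/22/20.** No text says so. Exclusion is the default result of the stated model when no missing-covariate rule is given. Imputation, a missing-indicator term or a constrained model would each keep these participants.
- **That their follow-up scores are in hand.** Collection is inferred from the schedule. No text confirms that people without a baseline score were given the questionnaire later, and some 4-month scores may not exist.
- **That the remedy recovers a 24% (or 10%) loss of precision.** Those figures, 1/√0.647 and 1/√0.825, compare complete-case analysis with having every baseline score. No model can restore unmeasured baselines. The gain available is the 5-19% in the working.

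The accrual figure is also soft. It comes from a schedule starting in April 2020, whereas enrolment began in June after a pandemic hold, and Wave 1 recruitment was still described as current on 2/22/21. Finally, a constrained longitudinal model is not the only adequate answer, so the fix allows an equivalent.

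**Conclusion.** The point holds as a minor one. By design, early Wave 1 participants lack a baseline score on a measure that the Protocol lists as secondary. The baseline-covariate rule and the all-randomized analysis cannot both be met for it without a further rule. Following the text literally gives a less precise, non-ITT analysis.

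The size rests on two assumptions, 63 to 127 participants affected and a baseline correlation of 0.5 to 0.7. Under these the complete-case standard error is about 5-8% larger at 63, and 13-19% larger at 127, than under a model that keeps everyone. A reader might infer a biased comparison or a threat to the trial's main result. Neither follows: missingness is set by calendar date, which is unrelated to arm under 1:1 randomization, and only one secondary questionnaire is involved.

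**What to change.** In SAP 9.4.4:

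1. State whether the Mindful Eating Questionnaire is an analysed outcome, and bring SAP Table 1 and Appendix A into line with Protocol Table 3.
2. If it is, analyse it with a constrained longitudinal model, in which baseline is one of the repeated outcomes with a common mean in both arms, or with an equivalent method that keeps participants without a baseline score. The estimand does not change.
3. Report the number of missing baseline scores by arm, and the number with a score at each follow-up visit.
4. Label any complete-case ANCOVA as a non-ITT sensitivity analysis.

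The cost is a dated SAP amendment and a different model statement for one secondary outcome. No new data are needed. SAP 9.4.1 records a review of the analysis in May 2025, so the amendment should say whether results for this questionnaire had been seen when it was written.

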Materials

- Omron Model HEM-907XL blood pressure monitor with small, medium, large, and extra large cuffs
- Tape measure

Note: The Omron cannot be used on arms with a circumference greater than 17" (large Omron cuff does not fit) or if the Omron is unable to take the measurement.

Procedure using the Omron

Set up

- Connect the AC adapter to the DC jack of the main unit and the electric outlet.
- Connect the air tube to the main unit by securing the air plug to the base of the air connector. This air tube is for use with the small, medium, and large cuffs only. The extra large cuff has its own non-detachable air tube for connection to the main unit.

Participant

- Should avoid caffeine, exercise, and smoking for at least 30 min before measurement.
- Invite participant to empty bladder before measurement .
- Shirt, blouse, or dress sleeves are loose fitting enough not to cause constriction of the arm even when pushed up for wrapping the cuff onto the bare arm. If too tight, the arm needs to be placed outside the sleeve.
- Remains quietly seated in a chair with both feet flat on the floor and back supported while measurements are taken. Neither the participant nor the staff should talk during the 5 min rest period or during the measurement.

Research Staff

- Apply the cuff to the right arm of the seated participant. **All BP measurements are made using the right arm unless prevented by injury or deformity.** If the left arm is used it is indicated on the BP and Heart Rate (BPHR) form and subsequent BP measures are taken using the left arm. See "How to Apply the Cuff" diagram.

- Measure the circumference of the largest part of the upper arm and select the cuff according to arm size.
 - ◀ 7"-9" small
 - ◀ 9"-13" medium
 - ◀ 13"-17" large
 - ◀ 17"- 20" extra large
- Connect the air tube and the cuff/bladder set by rotating the Luer connection.
- Place the participant's hand with the palm upward.
- Align the Artery Position Mark on the cuff with the brachial artery.
- Wrap the cuff snugly using both hands and securely fasten it with the Velcro™ tape. **The lower edge of the cuff should be placed ½" to 1" above the inner side of the elbow joint.**

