 - ◀ If the INDEX is positioned outside the RANGE, select the cuff suitable for the patient's arm circumference and wrap it again. Wrap the cuff so that you can insert only one finger between the cuff and arm. If the upper arm is more pyramid shaped rather than cylinder shaped it is necessary to wrap the cuff in a slightly diagonal fashion so that both the upper and lower borders of the cuff fit snugly against the skin.
- Keep the **level of the cuff at the same level as the heart** during the measurement. The participant should sit upright in the chair, not slouching, with arm supported (eg, resting on a desk)..
- Take the blood pressure.
 - Push the ON/OFF (power) BUTTON to turn on the power.
 - Set the MODE Selector to "AVG". The monitor has been programmed to:
 - ◀ Wait 5 min. until the 1st measurement.
 - ◀ Take 3 measurements.
 - ◀ Wait 1 min. between measurements.
 - Set the P-SET (inflation level setting) Knob to "AUTO".
 - Push the HIDE button for non-display of results.
 - Push the START Button to begin measurement. The 5 minute countdown will be displayed. After 5 minutes the monitor takes the first measurement and then displays the results. One minute later the 2nd measurement is taken. The monitor takes the 3rd and final measurement after another minute.
 - ◀ To stop a measurement, push the STOP Button. The unit will rapidly deflate.
 - ◀ Do not push the START Button without first wrapping the cuff around the participant's arm.
 - ◀ If an error occurs during measurement, the monitor will automatically start measurement again. If a second error occurs, measurement will automatically stop.
 - ◀ If the monitor determines that the pressure value is not correct, an error display appears (Er1 to 9). In this case, refer to Page 28 of the manual and start the measurement again.
 - ◀ **If the blood pressure is unattainable using the monitor the measure will be missing.**
Note this on the form by checking appropriate option 1) arm circumference greater than 17" 2) Omron unable to measure.
 - Push the HIDE button for display of results.
- Enter measurement results on the form.
 - After all 3 measurements are completed; the average value will be displayed.

- Enter the average pulse rate (BPM) on the form.
- Press the DEFLATION (deflation control) /Measurement Result Display Switch Button to display the 1st measurement for entering.
- Press the same button again to display the 2nd measurement for entering.

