## **7.2 Key Secondary Outcomes**

Key secondary outcomes include changes in the following outcomes from baseline to 24 months.

- blood pressure
- A1c

- markers of inflammation
- skin carotenoids
- self-reported dietary patterns

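### The blood pressure protocol contradicts itself on arms over 17 inches: one instruction leaves the reading missing, another supplies an extra large cuff for 17 to 20 inch arms, and neither is said to prevail.

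*Protocol*

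**What the plan says.** All the conflicting instructions stand in Protocol 8.1.3.2, Blood pressure protocol.

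**Pointing to a missing value above 17 inches**
- A note under Materials: "The Omron cannot be used on arms with a circumference greater than 17" inches. Its bracketed reason is that the large cuff does not fit; the extra large cuff is not mentioned.
- The missing-data rule in the procedure: "If the blood pressure is unattainable using the monitor the measure will be missing".
- The reason code on the form: "Note this on the form by checking appropriate option 1) arm circumference greater than 17" inches.

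**Pointing to a measurement between 17 and 20 inches**
- The equipment list: "Omron Model HEM-907XL blood pressure monitor with small, medium, large, and extra large cuffs".
- The set-up step: "The extra large cuff has its own non-detachable air tube for connection to the main unit".
- The cuff selection table, which gives the extra large cuff to arms of 17 to 20 inches.

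No section says which instruction takes precedence. The protocol amendment history (10.4) records a review of the whole protocol on 6/8/25, and the conflict remains in the current text.

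On the status of the outcome, SAP 7.2 states: "Key secondary outcomes include changes in the following outcomes from baseline to 24 months", and blood pressure is the first item listed. SAP 9.4.4 analyses it with ANCOVA methods similar to those for the primary outcome, controlling for the baseline value in addition to the primary-model covariates, which include baseline weight. The missing-data sensitivity analyses in SAP 6.6 are written for the weight contrast. Substitution from the health record (SAP 6.2) covers weights only. Nothing equivalent is specified for blood pressure.

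**The concern.** Large arms are to be expected in this trial. Patients are identified from the health record at a BMI of 30 or more, and the weight limit is just under 500 lb (Protocol 5.1). Protocol 9.4.2 also planned a subgroup with BMI above 40. A dedicated form code for arms over 17 inches shows that the team foresaw them.

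If staff used that code, blood pressure effects would not be estimated in the largest participants, even though a cuff for most of those arms is on the equipment list. If staff applied the two instructions differently from visit to visit, a participant could have a reading at one visit and a missing code at another with no change in arm size. Arm size also moves with weight, so part of the loss could be linked to what the intervention does. The plan has no remedy for blood pressure readings lost in this way.

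**Working it through.** **1. The plan's own figure.** Inputs from Protocol 9.2 and its Table 5: 360 randomised, 20% attrition, 80% power, alpha 0.05, SD of change 23.1 (systolic) and 11.1 (diastolic), stated detectable differences 7.6 and 3.6. The two-sided test is from SAP 9.4.4 and the 1:1 allocation from SAP 5.1.

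- Per arm: 360 × 0.8 / 2 = 144.
- Detectable difference = (1.960 + 0.842) × SD × √(2/n).
- Systolic: 2.802 × 23.1 × √(2/144) = 7.63, against 7.6 stated.
- Diastolic: 2.802 × 11.1 × √(2/144) = 3.66, against 3.6 stated.
- Effect size: 2.802 × √(2/144) = 0.330, against 0.33 stated.

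The planning figures reproduce.

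**2. Cost in precision if the 17-inch rule was applied.** The share of arms over 17 inches is not given. The table assumes a further loss on top of the 20% attrition.

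| Assumed further loss | n per arm | Detectable systolic | Detectable diastolic | Power for 7.6 mmHg systolic |
|---|---|---|---|---|
| 0% | 144.0 | 7.63 | 3.66 | 79.7% |
| 5% | 136.8 | 7.83 | 3.76 | 77.7% |
| 10% | 129.6 | 8.04 | 3.86 | 75.4% |
| 20% | 115.2 | 8.53 | 4.10 | 70.4% |

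If the cuff table was applied instead, nothing is lost between 17 and 20 inches. Arms over 20 inches are unmeasured under either instruction, so the loss due to the contradiction is smaller than the whole share over 17 inches.

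**3. Who would be lost, and whether that depends on weight change.** The planned model needs a baseline reading.

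- *Over 17 inches at baseline:* no baseline value, so the participant leaves the model whatever happens later. This depends on a pre-randomisation feature.
- *Over 17 inches at baseline, below it later:* a follow-up reading exists, but the baseline covariate is still missing, so it does not enter.
- *Under 17 inches at baseline, above it later:* the follow-up reading is lost because the arm grew. Only this group is lost according to post-randomisation weight change.

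**4. Illustrative size of the third group's effect.** A simulation used 60 trials of 4,000 participants for each scenario. Weight change was −5% against −1% with SD 7.3, the plan's own values. The rest was assumed:

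- arm circumference SD 1.6 inches, with 5, 10 or 20% above 17 inches at baseline;
- 0.05, 0.10 or 0.15 inches of arm per 1% weight change;
- 1 mmHg per 1% weight change, so the true effect is −4.0 mmHg;
- one follow-up visit, adjusted for baseline blood pressure and baseline arm size.

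In the middle scenario (10% and 0.10 inches), 1.7% of the intervention arm and 3.8% of the control arm crossed upward. The estimates were −3.96 with full data, −3.96 without those over 17 inches at baseline, and −3.75 without the upward crossers as well. Across all nine scenarios, losing the upward crossers attenuated the estimate by between 0.05 (3.944 − 3.891) and 0.55 mmHg (4.062 − 3.515). The baseline exclusion alone moved it by no more than about 0.03 mmHg, which is within simulation error.

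**The case against.** It can fairly be said that the missing code is only one side of a contradiction. The formal rule makes a reading missing only when the monitor cannot obtain it, and with the extra large cuff attached that need not be so at 17 to 20 inches. The note's reason speaks only of the large cuff and may be left-over text. The documents do not show that a single 17 to 20 inch arm went unmeasured. All of this stands, and it makes the loss conditional.

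A reader might infer something stronger: that the plan discards blood pressure in the heaviest participants, and that the arm losing more weight gains follow-up readings, so that missingness follows treatment. The documents do not support this. The cuff table tells staff to measure those arms. Readings regained by participants who shrink below 17 inches do not enter a model that requires a baseline value.

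The share affected is also an assumption. The BMI threshold of 30 applies to the record search; at the eligibility call and the enrolment visit, exclusion applies below 27.5 (Protocol 5.2 and 5.4). The weight ceiling is an exclusion limit, not a count of large arms.

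Finally, the SAP was drafted after all participants were randomised and refers to an analysis review in May 2025 (SAP 9.4.1), so a form change may recover no readings. That moves the weight of the remedy to reporting. It does not remove the contradiction or the absence of any missing-data plan for this outcome.

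**Conclusion.** The contradiction is certain: it is in the text of one section and concerns a listed key secondary outcome. Its effect is conditional on which instruction staff followed, which the documents do not say.

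If the note and form code were followed, the main consequence is that blood pressure results would not cover the largest participants, with some loss of power. The detectable systolic difference would rise from 7.6 to about 7.8 to 8.5 mmHg for assumed losses of 5 to 20%. The comparison between arms would remain balanced by randomisation for everyone excluded on baseline arm size. Bias related to weight change would be confined to those who pass 17 inches after baseline. It is probably small, at about 0.05 to 0.55 mmHg towards no difference, and that range rests on the simulation inputs above. The simulation has a single follow-up visit, so it gives no credit for readings at other visits that the planned longitudinal model would use.

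The documents do not support a claim of material bias in the treatment comparison. They also do not let a reader rule out that the heaviest participants are absent from the blood pressure results.

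**What to change.** 1. Reconcile the 17-inch note and form option 1 with the cuff table, so that the arm-size missing code applies only to arms that no supplied cuff fits (over 20 inches by the protocol's own table). This is a one-line change in two places, and the cuff is already listed.
2. State in the SAP or the report which instruction staff followed, and whether it changed during the trial.
3. Tabulate by arm and visit the readings coded missing for arm size. The reason code is already on the form, so this is one table.
4. If the count is not negligible, add one blood pressure sensitivity analysis that imputes missing readings, baseline included, using weight measured at the same visit. Weight is related to both arm size and blood pressure, so this addresses the upward crossers directly. An analysis restricted to participants with a baseline reading would largely repeat the planned ANCOVA and leave those crossers out. For participants never measured, the imputation extrapolates from smaller people and should be described as such.

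If collection is complete, items 2 and 3 are the main action, and item 1 corrects the record.
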